2.1.2 Full analysis set (FAS)

This analysis set comprises all randomized participants who received at least 1 dose of investigational product (IP), irrespective of their protocol adherence and continued participation in the study. Participants will be analysed according to their randomized treatment irrespective of whether or not they have prematurely discontinued, according to the intention-to-treat (ITT) principle.

All efficacy analyses will be performed using an ITT approach based on the FAS.

Demography and baseline characteristics will be summarized by treatment for the FAS. If there are major differences between the FAS and the safety analysis set, the summaries will be repeated and presented for the safety analysis set.

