Total Mucosa		/120											

Any participant with missing data at a specific time point will be considered as having a missing score at that time point.

The set of intercurrent events for this estimand consists of participants who use restricted medications, participants who have their OCS dose increased as rescue therapy after having previously achieved disease control and participants who withdraw from the study.

Participants who receive medications deemed to be intercurrent events as per Section [3.1.5.2](#) will have their last BPDAI activity score observed prior to the date of start of restricted medication carried forward to Week 36. If baseline is the last available assessment prior to the date of start of restricted medication, then it will be used to impute the missing data.

Likewise, participants who need to increase their OCS dose as a rescue therapy to treat their BP after having previously achieved disease control will have their last BPDAI activity score observed prior to the date of OCS dose increase recorded with start date > date of disease control assessment carried forward to Week 36. If baseline is the last available assessment prior to the date of OCS dose increase, then it will be used to impute the missing data.

For restricted medications/OCS during the study missing/partial start dates are not allowed. For participants who withdraw from the study without having rescue or restricted medications, missing BPDAI activity score at Week 36 will be imputed using multiple imputation based on participants who don't have rescue/restricted medication use. The same approach will be applied to those participants with missing data at Week 36 for any other reason. Further details are provided in Section [4.2.7.3](#). For the summary statistics, missing values will remain missing.

3.3.4 Change from baseline in BPDAI-Pruritus score at Week 36

The BPDAI-Pruritus is a continuous endpoint that will be completed at the visits specified in the CSP Table 2.

The BPDAI-Pruritus is a separate component of the BPDAI that asks the participant to grade the severity of pruritus over the past 24 hours, the past week, and the past month. For each recall period, severity of pruritus is rated on an NRS ranging from 0 for no itch to 10 for maximal itching.

The BPDAI-Pruritus score will be computed as the sum of the three components ranging from 0 to 30.

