	Treatment with benralizumab versus placebo, regardless of IP compliance	Cumulative OCS exposure (mg/kg) from baseline to Week 36 and from baseline to Week 16 (FAS)	
 • Treatment discontinuation – treatment policy • Restricted medication use – effectiveness (includes OCS dosing up to occurrence of event) • Study withdrawal – effectiveness (includes OCS dosing up to occurrence of event) 	Difference in mean cumulative OCS exposure (mg/kg) from baseline to Week 36 and from baseline to Week 16 (MMRM)	4.2.7.2

	Treatment with benralizumab versus placebo, regardless of IP compliance; rescue with OCS and restricted medication use indicate treatment failure	Change from baseline in BPDAI activity score at Week 36 (FAS), change from baseline in BPDAI-Pruritus score at Week 36 (FAS)	
 • Treatment discontinuation – treatment policy • Rescue with OCS^a – composite (LOCF) • Restricted medication use – composite (LOCF) • Study withdrawal – hypothetical (multiple imputation) 	Difference in mean change from baseline in BPDAI activity score/BPDAI-Pruritus score at Week 36 (ANCOVA)	4.2.7.3/ 4.2.7.4
Safety Objective: To compare the safety and tolerability of benralizumab with placebo in participants with symptomatic BP					
Safety	Treatment with benralizumab versus placebo, regardless of restricted medications.	
 • AEs • SAEs • Vital Signs • Physical examination (Safety) 	
 • Remained adherent to intervention (on-treatment) 	
 • Descriptive 	4.2.9

^a Rescue with OCS is defined as needing to increase OCS dose after previously having achieved disease control.

ANCOVA, analysis of covariance; BP, bullous pemphigoid; BPDAI, bullous pemphigoid disease area index; FAS, full analysis set; IP, investigational product; LOCF, last observation carried forwards; MMRM, mixed-effect model for repeated measures; OCS, oral corticosteroids.

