Sensitivity analyses might be conducted based on different missing data mechanism assumptions, including those expected to be more conservative, such as MNAR, to explore the robustness of any treatment effect, if the amount of missing data warrants further investigation. This might include utilizing multiple imputation approaches including the dropout reason-based multiple imputation where dropouts related to treatment are imputed using a jump to reference approach. Details using multiple imputation techniques are specified in Appendix 8.1.

Cumulative actual OCS exposure (mg) will be also summarized in an exploratory way using descriptive statistics by treatment group and 4 weekly interval, including the whole of the 36-week treatment period and the initial 16-week treatment period.

Daily OCS dose (mg/kg/day) will be also summarized in an exploratory way using descriptive statistics by treatment group and weekly interval from Week 2 to Week 36.

4.2.7.3 Change from baseline in BPDAI activity score at Week 36

The change from baseline in the total BPDAI activity score at Week 36 will be analysed by an ANCOVA model. More details on derivation rules and imputation rules to handle intercurrent events are given in Section 3.3.3.

The null hypothesis is: the mean for benralizumab is equal to the mean for placebo. Whereas, the alternative hypothesis is: the mean for benralizumab is not equal to the mean for placebo. That is:

$$H0: \text{Difference in means (benralizumab} - \text{placebo}) = 0$$

$$H1: \text{Difference in means (benralizumab} - \text{placebo}) \neq 0$$

The model will include change from baseline at Week 36 as the dependent variable, baseline BPDAI activity score as a continuous covariate and treatment and time of BP diagnosis as categorical covariates. Only patients with baseline and at least one post-baseline BPDAI activity score will be included in the model.

The model will be used to estimate, in terms of LS means, the mean change from baseline at Week 36 for each treatment group and the difference versus placebo, with corresponding 95% confidence limits. A p-value, corresponding to a 2-sided test, will be presented to compare the benralizumab and placebo treatment groups.

For participants who receive medications deemed to be intercurrent events as per Section 3.1.5.2 or need to increase their OCS dose as a rescue therapy will be imputed using a last observation carried forward (LOCF) method, as detailed in Section 3.3.3.

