For participants who withdraw from the study without having rescue or restricted medications, missing BPDAI activity score at Week 36 will be imputed using multiple imputation based on outcome of participants who don't have rescue/restricted medication use. The same approach will be applied to those participants with missing data at Week 36 for any other reason. Distributions will be modelled considering treatment group, time of BP diagnosis and values of BPDAI activity score observed at baseline and prior to the withdrawal/occurrence of intercurrent events.

Specifically, for a participant with missing observations after visit t, imputed observations value at visit t+n will be based on a model estimated from all participants who have an outcome observed at visit t+n conditioning on that participant's outcomes up to and including visit t.

Then, the overall estimate of treatment effect is obtained by using Rubin's rules [Rubin 1987] to combine the imputed outcomes using the ANCOVA model above specified.

In summary, the pattern mixture models will be implemented by multiple imputation via the following steps;

Step 1: Non-monotone missing data (usually relatively infrequent) will be imputed using the MCMC statement of SAS PROC MI under the MAR assumption. The following variables will be included in the imputation model: treatment group, time of BP diagnosis and BPDAI activity score from baseline to Week 36. Note: Dummy variables will be used for treatment and time of BP diagnosis. This will create a monotone missing pattern in the dataset within each treatment group. This step will create 100 imputed datasets.

Step 2: For participants who withdraw from the study without having rescue or restricted medications the values for each pattern will be imputed via the sequential regression method, using the MONOTONE REG statement of SAS PROC MI. The imputation model will be estimated from the observed data in participants without intercurrent events or need to increase their OCS dose as a rescue therapy and it will be used to impute missing observations in both treatment groups using the MNAR statement of SAS PROC MI. The following variables will be included in the imputation model: treatment group, time of BP diagnosis and BPDAI activity score from baseline to Week 36.

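### The BPDAI ANCOVA drops full-analysis-set participants who have no post-baseline score, although the SAP already says how to impute them

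*SAP*

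**What the plan says.** On who enters the model, SAP 4.2.7.3 states: "Only patients with baseline and at least one post-baseline BPDAI activity score will be included in the model".

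On the population, SAP 2.1.2 defines the FAS as "all randomized participants who received at least 1 dose of investigational product (IP), irrespective of their protocol adherence and continued participation in the study" and adds: "All efficacy analyses will be performed using an ITT approach based on the FAS". SAP Table 8 and protocol Table 10 both give the FAS as the population for the two Week 36 BPDAI endpoints. No post-baseline assessment is required for membership.

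On missing Week 36 scores, SAP 3.3.3 and 4.2.7.3 give three rules:
- Restricted medication: the last earlier score is carried forward, and "If baseline is the last available assessment prior to the date of start of restricted medication, then it will be used to impute" the missing value.
- Oral corticosteroid (OCS) rescue: the same, with "If baseline is the last available assessment prior to the date of OCS dose increase, then it will be used to impute the missing data".
- Withdrawal without either event: "missing BPDAI activity score at Week 36 will be imputed using multiple imputation based on outcome of participants" who had neither. The SAP then adds: "The same approach will be applied to those participants with missing data at Week 36 for any other reason".

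On baseline, SAP 3.1.1 leaves a missing baseline value missing and does not impute it.

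On changes, protocol 9.4.2.2 describes this ANCOVA without any post-baseline condition. SAP Section 1 says departures from the protocol are described in Section 6. Section 6 lists one change to this model, the removal of the severity covariate, and does not mention the inclusion condition.

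**The concern.** Having a post-baseline score is something that happens after randomization and treatment. Using it to decide who is analysed makes the analysed set smaller than the population in which the estimand is defined. It does so for steps 4 and 5 of the testing hierarchy in SAP 4.1.1: BPDAI activity directly, and BPDAI-Pruritus because SAP 4.2.7.4 adopts the 4.2.7.3 analysis. The two Week 16 analyses (SAP 4.2.8.8 and 4.2.8.9) adopt it as well, with nominal p-values.

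The two binary endpoints at steps 1 and 2 keep the same people, counted as non-responders or as not relapse-free (SAP 3.2 and 3.3.1). The analysed set would therefore change part of the way through one testing sequence.

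There is also a practical problem. For a participant with a baseline score only, one sentence says exclude and another says impute. A programmer cannot follow both, and the choice should not be left until after unblinding.

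**Working it through.** **The plan's own figure.** The plan attaches no number to this rule. The arm size of 50 comes from SAP 1.3, where it supports 85% power for the primary endpoint (50% against 20%, two-sided 5%). With a continuity correction:

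power = Φ{[0.30 − 1/50 − 1.96·√(2·0.35·0.65/50)] / √[(0.5·0.5 + 0.2·0.8)/50]} = Φ{(0.280 − 0.187)/0.0906} = Φ(1.03) = 84.8%.

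The 85% is reproduced, and nothing in this point changes it.

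**Side by side.** Take an FAS participant with a baseline BPDAI score.

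| Situation | Imputation rules | Inclusion sentence | Conflict? |
|---|---|---|---|
| Withdrew early, no later score, no rescue or restricted medication | Multiple imputation | Excluded | Yes |
| Did not withdraw, no later score for another reason | Multiple imputation | Excluded | Yes |
| Restricted medication, no later score | Baseline carried forward | Excluded | Yes |
| Restricted medication before the first post-baseline score, later score exists | Baseline carried forward | Included | No |
| OCS rescue | Last earlier score carried forward | Included if any later score exists | Almost never |

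The last row is nearly empty because rescue means a dose increase after disease control (SAP 3.1.5.1). Disease control is recorded at a visit, and BPDAI is scheduled at the same visits (protocol Table 2). A rescued participant should already have a post-baseline score.

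**Can the imputation run from baseline alone?** Yes. The SAP 4.2.7.3 model contains treatment, time of diagnosis, the baseline score and any earlier scores, and it works forward visit by visit. A baseline-only record is the earliest drop-out pattern.

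**Can such records arise?** Yes, though rarely. The first post-baseline window runs from Day 2 to Day 21 (SAP Table 2). A total is missing if any subscore is missing (SAP 3.3.3). The telephone follow-up option in protocol 7.1.1.1 does not name BPDAI scoring.

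**Size.** Each participant is 1/50 = 2% of an arm. The documents give no count. If 0 to 5% of 100 were baseline-only (an assumption), that is 0 to 5 people.

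Let k of 50 in one arm be baseline-only, with imputed mean change c, and let m be the mean change of the rest (negative is improvement). Ignoring covariate adjustment, including them moves that arm's mean by

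[(50 − k)m + kc]/50 − m = (k/50)(c − m).

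- *All k took restricted medication and had no later score.* Then c = 0. With m assumed between −30 and −50, k = 1 gives (1/50)(30 to 50) = +0.6 to +1.0 points, and k = 5 gives (5/50)(30 to 50) = +3.0 to +5.0. Inclusion makes the arm look less improved.
- *All k withdrew early.* Then c is close to u, the mean of event-free participants in the arm. If a fraction f of the rest had carried-forward events with mean e, then m = (1 − f)u + fe and c − m = f(u − e). With u = −50 and e = −30 (assumed), the shift is −20f·k/50: −0.4f points for k = 1 and −2.0f for k = 5, where f is below 1. Inclusion makes the arm look slightly more improved.

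The two cases have opposite signs, and the documents do not say which arm would hold the participants.

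**The case against.** The strongest reply is that the sentence hardly matters. Any post-baseline score at any later visit is enough to enter. Participants who stop treatment are asked to attend all visits to Week 36. BPDAI is also scored at discontinuation, unscheduled and follow-up visits (protocol 8.1.1.2). Both documents expect little missing data. The number affected may be zero.

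Nor does imputation do much for those affected. With baseline only, it conditions on treatment, time of diagnosis and baseline score, which are the terms of the ANCOVA itself. Its donors had no rescue or restricted medication, so it adds little information and does not correct for early leavers who differ from those who stayed. All of this stands, and it limits the size of the point.

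It might also be argued that an imputed score counts as a post-baseline score. The condition would then exclude nobody who has a baseline, and the sentence would have no purpose beyond the baseline requirement. That is a reason to remove the phrase.

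Two stronger readings are tempting, and the documents support neither:
- A reader might infer that the sentence overrides the baseline-carried-forward rule altogether. It does not. One sentence says who enters and the other says which value is used, and they coexist whenever a later score exists.
- A reader might infer that the exclusion favours benralizumab or differs by arm. Nothing in the documents shows an imbalance, and the working shows that the direction depends on why the scores are missing.

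**Conclusion.** Wrong as written (an internal contradiction), with low impact. The post-baseline condition removes FAS participants whom SAP 3.3.3 and 4.2.7.3 themselves say how to impute. It is absent from the protocol's model and is not declared in SAP Section 6. The conflict bites for early withdrawals, for scores missing for other reasons, and for restricted-medication users with no later score. OCS-rescue cases should be almost none.

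Requiring a baseline score is not at fault. It agrees with SAP 3.1.1, and eligibility already requires BPDAI at screening and randomization (protocol 5.1).

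Each affected participant is 2% of a 50-participant arm, and the number is probably very small. The illustrated shifts rest on assumed counts and assumed mean changes. The positive shifts hold only if every excluded person took restricted medication and had no later score, so they should not be read as the expected effect. The direction of any bias is unknown.

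**What to change.** In SAP 4.2.7.3, delete the requirement for a post-baseline score and keep the requirement for a baseline score. The sentence would then say that the model includes every FAS participant with a baseline BPDAI activity score, with Week 36 values handled by the rules in Section 3.3.3. State the same for BPDAI-Pruritus in 4.2.7.4, using the pruritus baseline, so that the Week 16 analyses follow. Report the number of baseline-only participants by arm.

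The cost is one sentence, a short cross-reference and a count, settled before unblinding. No new method is needed.

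The downside is that baseline-only participants would be imputed under missing-at-random from participants without rescue or restricted medication. This restores the estimand population but does not protect against non-random early exit. The missing-not-at-random sensitivity analyses in SAP 4.2.7.5 have to address that. They are conditional on the amount of missing data, so they should say explicitly that these participants are included.

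If the sponsor prefers to keep the restriction, it should be declared and justified in SAP Section 6 and paired with a sensitivity analysis that includes all FAS participants with a baseline score.

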### **Change from baseline in BPDAI activity score at Week 36**

BPDAI activity score is a continuous endpoint that will be completed at the visits specified in the SoA ([Table 2](#)) during the initial 36-week treatment period.

The estimand strategy is outlined in [Table 10](#) above. For this endpoint, intercurrent events of rescue use with OCS after having previously achieved disease control and restricted medication use are considered unfavorable outcomes and will be handled with a composite strategy whereby participants experiencing these events prior to Week 36 will have their last observation prior to rescue/restricted medication use carried forward to Week 36. For participants who discontinue the study without having rescue or restricted medications, missing data at Week 36 will be imputed using multiple imputation based on participants who don't have rescue/restricted medication use. Once these imputations are made, the available change from baseline in BPDAI score at Week 36 will then be analyzed using an analysis of covariance (ANCOVA) model.

The model will include change from baseline at Week 36 as the dependent variable, baseline BPDAI score as a continuous covariate, and treatment, baseline disease severity, and time of

BP diagnosis as categorical covariates. The model will be used to estimate the mean change from baseline at Week 36 for each treatment group and the difference versus placebo, with corresponding 95% confidence limits. A p-value, corresponding to a 2-sided test, will be presented to compare the benralizumab and placebo treatment groups.

To support this analysis, observed means and mean changes from baseline will be summarized using descriptive statistics by treatment group and each scheduled visit up to Week 36. In addition, the cumulative distribution function of absolute changes from baseline in BPDAI activity score at Week 36 will also be plotted, to allow the treatment difference at various response thresholds to be explored. Responder analyses using minimal clinically important differences presented in the literature ([Wijayanti et al 2017](#)) may be presented, if appropriate.

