### **Change from baseline in BPDAI-Pruritus score at Week 36**

BPDAI-Pruritus score is a continuous endpoint that will be completed at the visits specified in the SoA ([Table 2](#)) during the initial 36-week treatment period. The statistical analysis described above for BPDAI activity score will be carried out for this endpoint, with the same estimand approach and the same ANCOVA model will be fitted to these data.

To support this analysis, observed means and mean changes from baseline will be summarized using descriptive statistics by treatment group and each scheduled visit up to Week 36. In addition, the cumulative distribution function of absolute changes from baseline in BPDAI-Pruritus score at Week 36 will also be plotted to allow the treatment difference at various response thresholds to be explored.

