1 STUDY DETAILS

This statistical analysis plan (SAP) outlines the analyses to be generated for the global clinical study report (CSR). Additional analyses required for regional submissions will be prespecified in a separate analysis plan and will be submitted to the appropriate authorities.

The current SAP focuses on the double-blind study period with a high-level description of the descriptive analysis for the open-label extension (OLE) analysis. If required, additional details regarding descriptive analyses in the OLE period will be provided in a separate OLE SAP.

The SAP describes the statistical analyses specified in the clinical study protocol (CSP); any changes with regards to what is already specified in the CSP will be described in Section 6.

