4.1.2 Stratification and subgroup variables

Statistical models will include stratification factors to properly handle the possible variation of treatment effect within the strata, as detailed in Section [4.2](#).

Exploratory analyses will be also carried out to explore the uniformity of the detected overall treatment effect across key, pre-defined, subgroups. These analyses will focus on the primary endpoint, and they may be performed on key secondary endpoints if deemed appropriate. If a small number of participants are in a subgroup, only descriptive statistics will be reported, and formal comparisons might not be performed.

The following stratification and/or subgroup variables are defined:

Disease severity (Moderate, Severe)

The BPDAI activity score at baseline will be used to assess disease severity, whereby participants with a score greater than or equal to 56 points will be classified as severe.

Time of BP diagnosis (Participants newly diagnosed, Participants previously diagnosed and relapsing)

A participant is defined as newly diagnosed if the participant is enrolled during the first episode of BP, and this episode hasn't been controlled prior to the study. The number of relapses in the past 2 years as collected in the eCRF is equal to zero.

A participant is defined as previously diagnosed and relapsing if the participant is enrolled during a relapse of BP. In this case the number of relapses in the past 2 years as collected in the eCRF is ≥ 1 .

Time of BP diagnosis and recurrence treatment (Participants newly diagnosed, Participants previously diagnosed and relapsing on OCS, Participants previously diagnosed and relapsing off OCS)

Participants newly diagnosed will be identified as detailed above, while participants previously diagnosed will be further classified into:

Previously diagnosed and relapsing on OCS, if the participant most recent relapse occurred whilst the participant was on OCS, during tapering, or within 2 months of tapering off OCS.

Previously diagnosed and relapsing off OCS, if the participant most recent relapse occurred whilst the participant had been off OCS for more than 2 months.

Age group (at informed consent, < 65 years, ≥ 65 years and < 75 years, ≥ 75 years)

Age will be derived from the date of informed consent - date of birth, rounded down to the nearest integer. For participants in countries where date of birth is not recorded, the age as recorded in the eCRF will be used.

Gender (male, female)

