Step 3: For participants who receive medications deemed to be intercurrent events or need to increase their OCS dose as a rescue therapy the missing values for each pattern will be replaced by the last observation carried forward.

Step 4: The imputed data from Step 1, Step 2 and Step 3, along with observed data will be combined to create 1000 complete dataset which will then be analysed using the main ANCOVA statistical model.

Step 5: The estimates from multiple imputed datasets will be combined using Rubin's combination rules for statistical inference (using PROC MI ANALYZE).

The seed used will be 88281 for both steps 1 and 2.

To support this analysis, observed means and mean changes from baseline will be summarized at each scheduled visit up to Week 36 using descriptive statistics by treatment group. The same descriptive approach will be used to summarize results for the total BPDAI damage score.

To explore the uniformity of the detected overall treatment effect, the model might also be fitted considering baseline variables and their interaction with treatment as additional covariates.

In addition, the cumulative distribution function of absolute changes from baseline in BPDAI activity score at Week 36 will also be plotted, to allow the treatment difference at various response thresholds to be explored. Responder analyses using minimal clinically important differences presented in the literature ([Wijayanti et al 2017](#)) may be presented, if appropriate.

4.2.7.4 Change from baseline in BPDAI-Pruritus score at Week 36

The change from baseline in the BPDAI-Pruritus score at Week 36 will be analysed by a ANCOVA model. More details on derivation rules and intercurrent events are given in Section [3.3.4](#).

The statistical analysis described in Section [4.2.7.3](#) for BPDAI activity score will be carried out for this endpoint using 88381 as the seed. In the MI models however, baseline disease severity will be added as categorical covariate.

To support this analysis, observed means and mean changes from baseline will be summarized at each scheduled visit up to Week 36 using descriptive statistics by treatment group.

In addition, the cumulative distribution function of absolute changes from baseline in BPDAI activity score at Week 36 will also be plotted, to allow the treatment difference at various response thresholds to be explored.

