6 CHANGES OF ANALYSIS FROM PROTOCOL

Section 2.1.5 OLE analysis set has been added to identify all participants who enter into the OLE period.

In Section 3.1.5.2 further detail around which restricted medications are considered intercurrent events has been provided.

In Section 3.2 the missing data handling strategy for the primary endpoint has been detailed to cover occurrences of missing disease state assessments between two non-missing assessments. This is to integrate and not to change the approach specified in the CSP that states: “Any participant with missing data at a specific time point will be considered as a non-responder at that time point.” This statement in the CSP is meant to be applied to any missing disease state assessment after the last non-missing assessment.

In Section 4.2.7.3 the ANCOVA model specified for the analysis of the change from baseline at Week 36 in BPDAI activity score has been changed removing baseline disease severity as categorical covariate. This categorical variable is derived based on the baseline BPDAI activity score which is already included in the model as continuous covariate.

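### As written, the SAP drops disease severity, a randomization stratum, from the BPDAI-Pruritus ANCOVA; the protocol model includes it and SAP Section 6 declares no such change

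*SAP*

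**What the plan says.** **Protocol.** Section 6.3.1 stratifies randomization by disease severity (moderate or severe, cut at a BPDAI activity score of 56) and by time of BP diagnosis. In Section 9.4.2.2 the ANCOVA for the BPDAI activity score has "baseline BPDAI score as a continuous covariate, and treatment, baseline disease severity, and time of" diagnosis as its terms. For BPDAI-Pruritus the same section says "the same ANCOVA model will be fitted to these data". The protocol's pruritus model therefore contains severity.

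**SAP.** Section 4.2.7.3 gives the activity ANCOVA with "baseline BPDAI activity score as a continuous covariate and treatment and time of BP diagnosis as categorical covariates", so severity is gone. Its Step 4 produces completed datasets "which will then be analysed using the main ANCOVA statistical model". Section 4.2.7.4 applies this analysis to BPDAI-Pruritus with a different seed and adds: "In the MI models however, baseline disease severity will be added as categorical covariate". It does not restate the ANCOVA terms.

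**Change control.** SAP Section 1 says "any changes with regards to what is already specified in the CSP will be described in Section 6". Section 6 lists the removal of severity from the activity-score ANCOVA, with the reason: "This categorical variable is derived based on the baseline BPDAI activity score which is already included in the model as continuous covariate". It lists no model change for pruritus.

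**The concern.** The Section 6 reason is sound for the activity score, because severity is that score cut at 56. It does not carry over to pruritus, a separate patient-reported score from 0 to 30: a model adjusted for baseline pruritus does not contain the severity stratum in any form. The sentence about the MI models suggests that the authors saw the need to restore severity for this endpoint but wrote it for the imputation step only.

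BPDAI-Pruritus is fifth of the six tests in the hierarchy, and failure there also stops the Week 16 OCS test. The Week 16 pruritus analysis (SAP 4.2.8.9) inherits the same model. Two things are at stake: precision on a confirmatory endpoint, and having a single pre-specified model, so that nobody has to choose between two readings after unblinding.

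**Working it through.** **1. Which model does the text specify?** The plan gives no figure to reproduce here, so the first step is to compare the texts.

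| Endpoint in the hierarchy | Severity in the test model (SAP) |
|---|---|
| Complete remission off OCS (4.2.6.1) | Yes |
| Relapse-free (4.2.7.1, same method as the primary) | Yes |
| Cumulative OCS, Weeks 36 and 16 (4.2.7.2) | Yes |
| BPDAI activity (4.2.7.3) | Carried by baseline activity |
| BPDAI-Pruritus (4.2.7.4) | Imputation models only, on the natural reading |

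Steps 1 and 2 of 4.2.7.3 list the variables of the imputation model. Step 4 then sends the completed data to a separately named ANCOVA. On those terms, the models that gain severity in 4.2.7.4 are the imputation models. Pruritus is then the only tested endpoint with severity in no form in its analysis model.

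**2. What does leaving the stratum out cost?**

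Inputs from the documents: about 50 per arm (SAP 1.3), a 2-sided 5% test, and the two strata.

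Assumed, because the documents do not give them: residual SD 7, treatment effect 4 points, half of participants severe (30% as a variant), a severity effect of 0 to 7 points given baseline pruritus, permuted blocks of 4, and complete data (no LOCF or imputation).

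*Analytic.* Stratified randomization balances severity across arms, so severity adds nothing to the true variance of the treatment difference. If it is left out of the model, its variance goes into the residual, and the reported standard error is too large by about

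SE ratio = sqrt(1 + p(1 − p)d²), with p the share severe and d the severity effect divided by the SD.

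- p = 0.5, d = 4/7 = 0.571: sqrt(1 + 0.25 × 0.327) = 1.040
- p = 0.5, d = 1: sqrt(1 + 0.25) = 1.118
- p = 0.3, d = 1: sqrt(1 + 0.21) = 1.100

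*Simulation.* 8,000 trials per setting, half severe, comparing the ANCOVA on treatment, baseline pruritus and time of diagnosis without and with severity:

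| Severity effect (points) | Mean SE, without / with | SE increase | Power %, without / with | Type I error %, without / with |
|---|---|---|---|---|
| 0 | 1.403 / 1.404 | 0% | 80.2 / 80.1 | 5.1 / 5.1 |
| 1 | 1.406 / 1.403 | 0.2% | 79.4 / 79.7 | 4.9 / 5.0 |
| 2 | 1.415 / 1.402 | 0.9% | 79.8 / 80.5 | 5.0 / 5.1 |
| 3 | 1.435 / 1.404 | 2.2% | 78.8 / 80.1 | 4.3 / 4.9 |
| 4 | 1.460 / 1.406 | 3.8% | 78.0 / 80.3 | 4.1 / 4.9 |
| 5.5 | 1.509 / 1.406 | 7.3% | 75.1 / 79.3 | 3.5 / 4.7 |
| 7 | 1.566 / 1.405 | 11.5% | 72.4 / 79.6 | 3.1 / 4.8 |

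With 30% severe, the SE increase at 2, 4 and 7 points is 0.8%, 3.3% and 9.9%, and power is 79.8 / 80.3, 77.8 / 79.7 and 74.0 / 79.8. The mean estimates of the two models differ by at most 0.003 point, so there is no bias.

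**3. Cross-check on another scale.** If severity explains a share R² of the residual variance, the SE ratio is 1/sqrt(1 − R²): 1.026 at 0.05, 1.054 at 0.10 and 1.118 at 0.20. The case p = 0.5, d = 1 corresponds to R² = 0.25/1.25 = 0.20, so the two scales agree.

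**The case against.** Four points can be made for the SAP.

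- **The phrase may mean the ANCOVA run on the imputed data.** Elsewhere the SAP uses the term categorical covariate for analysis models, while the imputation steps speak of variables and dummy variables. On that reading severity stays in the pruritus ANCOVA, and Section 6 is silent because nothing changed. This is possible, but Step 4 of 4.2.7.3 names the ANCOVA separately from the imputation model. If it was the intent, the same clarifying sentence is needed.
- **A strictly literal carry-over would adjust pruritus for baseline activity,** which largely carries severity. That would leave baseline pruritus out of the pruritus model and make adding severity to the imputation models largely redundant. It does stand that 4.2.7.4 leaves the baseline covariate unnamed as well.
- **The SAP 4.1.2 rule is not absolute.** It reads "Statistical models will include stratification factors to properly handle the possible variation of treatment effect within the strata", but the sentence goes on to defer to Section 4.2 for the detail. This stands: the rule shows intent and does not by itself prove a breach.
- **The effect is small and rests on assumptions.** This also stands. Nothing in the documents supports a severity effect as large as 1 SD after adjustment for baseline pruritus, and the simulation does not model LOCF or imputation. Up to 4 points, the power loss is about 0 to 2 points.

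**Conclusion.** The concern holds on the natural reading of the SAP. The pruritus ANCOVA omits a stratification factor that the protocol includes, the change is not declared, and the only stated reason for dropping severity applies to a different endpoint. Other readings are possible but fit the text less well, and the section does not settle them.

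The validity of the test is not threatened: there is no bias, and type I error without the term ran from 3.1% to 5.1%. The cost is precision, and only if severity predicts Week 36 pruritus given baseline pruritus. The likely loss is small (up to about 2 power points for effects up to 0.6 SD), and reaches about 7 points only at the 1 SD upper end. All of these sizes depend on the assumed SD, treatment effect, share severe and severity effect. The case for changing the text is that the correction is nearly free and fixes one confirmatory model before unblinding.

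**What to change.** In SAP 4.2.7.4, write the ANCOVA out: change in BPDAI-Pruritus regressed on treatment, baseline BPDAI-Pruritus score (continuous), baseline disease severity and time of BP diagnosis. Keep severity in the imputation models, and describe those separately. This restores the protocol's model and names the baseline covariate; Week 16 follows through the cross-reference in 4.2.8.9. If leaving severity out was intended, Section 6 should declare it for pruritus and give a reason specific to that endpoint.

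The cost is one sentence and one degree of freedom. With no association between severity and pruritus, the extra term changes the standard error from 1.403 to 1.404 under the assumptions above.
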